The single or double freeze modalities were chosen given the results of the UH2 trial where single-freeze CryoPen® achieved a greater depth of necrosis than double freeze, and the WHO cryotherapy guidelines which endorse CO₂ double-freeze as the standard cryotherapy treatment. While these are the preferred modalities, in a few cases clinicians may decide to repeat the CryoPen® modality to correct placement of the first application and maximize treatment efficacy and patient safety.

We will approach approximately 1,602 women with CIN2+ during a 2.5 year enrollment phase (30 months). Assuming an approximately 80% participation rate, ¹⁰ approximately 1,281 women will be enrolled—1,152 (90%) will be eligible for cryotherapy (i.e. no contraindications) and 129 will be ineligible and undergo alternative treatments. We estimate that approximately 20% will be lost to follow-up at the twelve-month visit, so that we will have complete data on a total of 922 women (57.5% of 1,602) treated with either CO₂-based cryotherapy, LMIC-adapted CryoPen®, or thermoablation. We will monitor the percentages of ineligibles, contraindications, and loss to follow-up in real time and adjust recruitment accordingly to achieve the target sample size. In addition, we will conduct a non-essential 6-week follow-up visit to evaluate adverse effects from the ablative procedures. The primary endpoint of the study will be to determine residual disease at a 12-month follow up visit as determined by colposcopy and four-quadrant biopsies.

Enrollment and Treatment

Enrollment diagnosis will be based on the local pathology. These slides will be read by an expert gynecologic pathologist for quality assurance. At the pre-treatment visit, consented women will be administered a short questionnaire to collect demographic

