Statistical Power and Sample Size. With a total of 922 women with a diagnosis of CIN2+, 307 per treatment arm, the study will have at least 80% power (alpha = 0.05) to detect a non-inferiority margin difference of 10% between the cure fraction of CO₂-based cryotherapy (reference) and of the LMIC-adapted CryoPen® (experimental) and the WISAP thermoablator (experimental), for a range of efficacy (50% to 80%) for the reference treatment and 40% efficacy under the null hypothesis of inferiority. We chose a range of 50-80% efficacy for cryotherapy because although the literature suggests CO₂-based cryotherapy is 80% effective, the disease ascertainment by colposcopy following treatment in previous studies was before the recognition that colposcopy is not perfectly sensitive. Therefore, the disease ascertainment in those studies was not as rigorous as proposed in this study. To ensure that the study is sufficiently powered for a wide range of efficacies, we are selecting 50% efficacy for the control arm as the worst-case scenario for study power. In order to achieve a sample size of 922 with complete follow-up, we will enroll 1281 women with CIN2+ under the assumption that 10% will have contraindications for cryotherapy and 20% will be lost to follow-up at twelve months post-treatment.

Test of cure

Analytic Approach. Since all women returning for the twelve-month visit will undergo four-quadrant biopsies and LEEP if diagnosed with CIN2+, regardless of the baseline characteristics or ablative treatment, we can assess the test of cure performance (sensitivity, specificity, positive predictive values (PPV), and negative predictive values (NPV)) of each test (VIA, cytology, and high-risk HPV DNA) for recurrent CIN2+ and CIN3 diagnosed by local and expert pathology. Performance will be stratified by quartiles of age and by the baseline diagnosis. McNemar chi-square will be used to test whether differences in sensitivity and specificity are significant (p < 0.05). A method developed by Leisenring *et al.* ¹² will be used to test for significant differences in PPV and NPV.

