Statistical Power. The statistical power for comparing sensitivity for the test of cure for VIA, cytology, and high-risk HPV testing is dependent on sample size of the efficacy study and the actual efficacy. We are enrolling 1281 women to assure that we have 930 women with a twelve-month follow-up. The larger the number of women who return for their follow-up, the larger the sample size for a given level of efficacy will be. The more efficacious the treatments, the smaller the sample size will be. Assuming 70% efficacy in treatment (30% recurrence), results of tests for cure will be available for 279 women with recurrence. This will provide 85% power (0.05 two-sided alpha) to detect a 10% difference in sensitivity between tests assuming 20% discordance between tests.

Interim Analysis of Cure Fractions. An interim analysis of cure fractions will be performed after approximately 2 years of study opening, when approximately 1/3 of the women have been enrolled. A confidence interval will be calculated for the difference (LMIC-adapted CryoPen® minus CO₂-based cryotherapy and WISAP thermoablator minus CO₂-based cryotherapy) in cure fractions. If the upper bound of the confidence interval is lower than the non-inferiority margin (-10%), then treatment modification or termination may be considered. The confidence interval will be calculated using an alpha calculated using an alpha time-squared spending function to maintain an overall 5% Type I error (one-sided).

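### The 85% test-of-cure power does not follow from its inputs: 279 recurrences, a 10-point difference and 20% discordance give about 96–97%; 85% needs about 30% total discordance

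*Combined protocol and SAP*

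**What the plan says.** Section 3.2, under Test of cure, gives the only power statement for comparing the three follow-up tests. It takes 930 women at twelve months, assumes 70% efficacy (30% recurrence), and concludes that "results of tests for cure will be available for 279 women with recurrence". It then states: "This will provide 85% power (0.05 two-sided alpha) to detect a 10% difference in sensitivity between tests assuming 20% discordance between tests". The same paragraph makes clear that the figure depends on efficacy: "The more efficacious the treatments, the smaller the sample size will be".

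The Analytic Approach for Test of cure names the method: "McNemar chi-square will be used to test whether differences in sensitivity and specificity are significant", at p < 0.05. No multiplicity adjustment, power formula or split of the discordance into its two cells is given.

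Two other statements bear on the inputs. The primary sample-size paragraph in Section 3.2 plans "for a range of efficacy (50% to 80%) for the reference treatment". Section 3.1 expects that "we will have complete data on a total of 922 women", whereas the test-of-cure paragraph says "We are enrolling 1281 women to assure that we have 930 women with a twelve-month follow-up".

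**The concern.** Power for a McNemar test at a given alpha is fixed by three numbers: the number of pairs, the difference between the two discordant proportions, and their sum. The plan gives all three, so its 85% can be checked directly. A 10-point difference is half of a 20% total discordance, which is a strongly one-sided split, and with 279 pairs that should give power well above 85%.

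Either the power is wrong for the stated discordance, or the 20% is something other than the total and is not labelled as such. The distinction matters because HPV test sensitivity after ablation is a secondary objective (Section 2.0), and Section 3.1 sets the goal of finding which of the three tests is most sensitive. The number of recurrences falls as treatment works better, so a reader needs to know which discordance was assumed to judge how the comparison holds up at higher efficacy.

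**Working it through.** **Inputs** (all from Section 3.2)
- Pairs: n = 0.30 × 930 = 279 women with recurrence.
- Difference in sensitivity: d = 0.10.
- Two-sided alpha 0.05, so z = 1.96.
- Discordance: 20%. Write ψ for the sum of the two discordant cells. The larger cell is (ψ + d)/2 and the smaller is (ψ − d)/2.
- Stated power: 85%.

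**Formula** (normal approximation to McNemar's test)

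Power = Φ[(d√n − 1.96√ψ) / √(ψ − d²)]

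**Attempt to reproduce 85% with 20% as the total.** The cells are 15% and 5%.
- d√n = 0.10 × √279 = 1.670
- 1.96√0.20 = 0.877
- √(0.20 − 0.01) = 0.436
- (1.670 − 0.877)/0.436 = 1.82, and Φ(1.82) = 96.6%

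Full enumeration takes the number of discordant pairs as Bin(279, 0.20) and, given m such pairs, the larger cell as Bin(m, 0.75). It gives 96.3% for the exact test, 97.2% for the uncorrected chi-square and 96.2% with continuity correction. None is near 85%.

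**With 20% as the larger cell.** The cells are 20% and 10%, so ψ = 0.30.
- 1.96√0.30 = 1.074
- √(0.30 − 0.01) = 0.539
- (1.670 − 1.074)/0.539 = 1.11, which gives 86.6%

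Enumeration gives 84.7% exact, 87.3% uncorrected and 84.5% continuity-corrected. This is close to the plan's figure.

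**Solving for 85% at n = 279 and d = 0.10.** The total discordance must be 31.4% (normal), 29.7% (exact) or 32.0% (uncorrected).

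**Other possible sources, holding ψ = 0.20**
- Alpha divided by three for three pairwise comparisons: 91.6% normal, 91.0% exact.
- Alpha 0.01: 88.3% normal.
- 277 recurrences (0.30 × 922 = 276.6) instead of 279: 96.5% normal, 96.2% exact.
- A difference of 8 points rather than 10: 85.2% normal, 83.2% exact, but this contradicts the stated difference.

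**What the ambiguity does across efficacy.** Power is shown as normal / exact, with recurrences taken from 922 completers and d = 0.10.

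| Efficacy | Recurrences | 20% total (15% and 5%) | 30% total (20% and 10%) |
|---|---|---|---|
| 50% | 461 | 99.8% / 99.8% | 97.7% / 97.4% |
| 60% | 369 | 99.2% / 99.2% | 94.2% / 93.4% |
| 70% | 277 | 96.5% / 96.2% | 86.4% / 84.4% |
| 77% | 212 | 91% / 90% | 76% / 73% |
| 80% | 184 | 86.5% / 84.2% | 70.0% / 66.3% |

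The 77% row is the lower end of the CIN3 cure range that Section 9.0 cites for cryotherapy.

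Power of 85% needs 177 recurrences (normal) or 188 (exact) at 20% total discordance, which corresponds to 80.8% or 79.6% cure among 922. At 30% total it needs 267 or 282, which corresponds to 71.0% or 69.4% cure.

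**The case against.** The best defence is that nothing was miscalculated. The text does not use the word total, and reading 20% as the larger discordant cell brings power to within 2 points of 85%. On that view the input is under-specified, not wrong. This is a plausible account of where the figure came from, but it does not rescue the sentence. Discordance between two tests ordinarily means all disagreements, and a reader who takes it that way gets a power 11 points away. Whichever number is at fault, the sentence needs the same correction.

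A second defence is that the consequence is small. This part largely stands. The comparison serves a secondary objective, no decision rule uses the 85%, and on the ordinary reading the plan understates its power, which is the safe direction. The power is explicitly conditional on 70% efficacy, and the paragraph itself warns that better treatment leaves fewer recurrences. The 50–80% range was set for the reference arm in the non-inferiority calculation, not for recurrence pooled over three arms, and Section 3.2 argues that stricter ascertainment may lower the observed efficacy. At 50–70% efficacy both readings give at least about 84%.

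Even so, efficacy of 77–80% lies within figures the document itself cites. There the two readings differ by about 15 to 18 points, and the warning about efficacy cannot be applied without knowing the discordance assumed.

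**Conclusion.** The concern holds. With 279 recurrences, a 10-point difference, two-sided alpha 0.05 and 20% total discordance, McNemar power is 96–97%, not 85%. About 85% is obtained with roughly 30% total discordance, most simply 20% against 10%. The documents do not show which was intended, so either the power or the discordance is mis-stated.

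The conclusion rests on a paired McNemar test, as planned, with no multiplicity adjustment, and it does not depend on the power method or on using 922 in place of 930. At 70% efficacy the comparison is adequately powered on either reading. At 80% efficacy it remains so at 20% total discordance (about 84–86%) but not at 30% (about 66–70%). The trial's sample size, set by the primary comparison, is not affected. The correction should be made, but it does not threaten the trial.

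**What to change.** In Section 3.2, Test of cure, replace the power sentence with one that gives both discordant cells, names the method (normal approximation or exact McNemar), and uses the 922 planned completers, i.e. 277 recurrences at 70% efficacy. The number 922 follows from the plan's own attrition: 1,152 × 0.80 = 921.6. Depending on what was intended, the sentence should state one of these:

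- about 96% power, assuming 20% total discordance (15% and 5%); or
- about 84–86% power, assuming 30% total discordance (20% and 10%).

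Optionally, add one row giving power at 50, 60, 70 and 80% efficacy for the chosen discordance, using the figures tabulated above.

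The cost is one sentence, and one table row if wanted. No extra patients are needed, and the test and endpoint do not change.

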12.0 Study and safety monitoring

The PI and the study coordinators are staff members of the institutions participating in the study; general study supervision will be conducted by the PI. The local study coordinators will conduct recruitment, consent, and interviews of potential study participants. Sample labeling will be conducted by the study coordinators. The patient database will be managed by the research staff secretary and/or study coordinators. The PI and study coordinators will conduct adverse events monitoring.

Data and Safety Monitoring Plan. Participants will include the principal investigator and study co-investigators, in addition to an epidemiologist, an OB-GYN, a gynecologic oncologist, and 2 researchers who are not part of the study. After enrollment begins, the group will meet bi-monthly by telephone conference and additionally if any unanticipated Adverse Events (AEs), Serious Adverse Events (SAEs), or Unanticipated Problems (UPs) occurs. They will assess enrollment, loss to follow-up, any safety issues or concerns including pain due to treatment, and perform an interim analysis.

Interim Analysis of Cure Fractions. An interim analysis of cure fractions will be performed after two years from study opening when approximately 1/3 of the women have been enrolled. Confidence intervals will be calculated for the differences (LMIC-adapted CryoPen® minus cryotherapy and WISAP thermoablator minus cryotherapy) in cure fractions. If the upper bound of the confidence interval is lower than the non-inferiority margin (-10%), then treatment modification or termination may be considered. The confidence interval will be calculated using an alpha calculated using an alpha time-squared spending function to maintain an overall 5% Type I error (one-sided).

13.0 Managing and reporting adverse events and unanticipated problems 13.1 Adverse Events and Unanticipated Problems

An **adverse event (AE)** is any untoward or undesirable event experienced by a participant regardless of whether the event is expected or related to the participant's involvement in the research.

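### The interim look at 12-month cure is timed by calendar and enrolment instead of by a number of 12-month results, and its two timing conditions do not fit a steady 30-month accrual

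*Combined protocol and SAP*

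**What the plan says.** Section 3.2 (Interim Analysis of Cure Fractions) places the look "after approximately 2 years of study opening, when approximately 1/3 of the women have been enrolled". Section 12.0 repeats it almost word for word: "after two years from study opening when approximately 1/3 of the women have been enrolled". The quantity compared is the cure fraction. It exists only after the 12-month visit (section 3.1) and after the local and expert pathologists have reached consensus (section 5.3).

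Section 3.1 plans recruitment "during a 2.5 year enrollment phase (30 months"), in which "approximately 1,281 women will be enrolled", 1,152 are eligible for ablation, and 922 have complete data after 20% loss. It also says that eligibility and losses will be monitored "in real time and adjust recruitment accordingly to achieve the target sample size". Women who miss the 12-month visit are pursued until 18 months after treatment.

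The interim interval uses an "alpha time-squared spending function to maintain an overall 5% Type I error (one-sided"). If its upper bound lies below −10 points, "treatment modification or termination may be considered". Neither section gives a number of results, an information fraction or a nominal alpha.

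For the final analysis, section 3.2 uses 95% confidence intervals for the differences, and claims at least 80% power at alpha 0.05 with 307 per arm, without saying whether that alpha is one- or two-sided.

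**The concern.** A look at a 12-month endpoint is only as informative as the number of women who have that endpoint. Here the look is tied to a date and to enrolment, and neither fixes that number. The two conditions are also hard to satisfy together with the stated enrolment period. This is the only formal comparison of cure that the plan schedules before the end, in a trial that tests two devices against a reference. If the look falls with few results, it has little chance of showing even a large deficit.

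The boundary is not reproducible either. Time in the spending function could mean calendar time, share enrolled or share of results, and the only fraction in the text is a share of enrolment. Two analysts could set different boundaries on the same data.

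**Working it through.** **Inputs from the documents.** 1,281 enrolled, 1,152 randomised, 922 results (307 per arm), 30 months, 20% loss, margin 10 points, overall 5% one-sided for the interim. The enrolment chain reproduces: 1,602 × 0.8 = 1,281.6; 1,281 × 0.9 = 1,152.9; 1,152 × 0.8 = 921.6.

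**Assumptions.** Constant monthly accrual from opening, equal arms and, unless stated otherwise, returns at exactly month 12. Time-squared spending is read as 0.05 × t².

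**When the conditions are met.**
- Accrual over 30 months: 1,152/30 = 38.4 per month. One third is 1,152/3 = 384, reached at 384/38.4 = month 10. At month 24, 38.4 × 24 = 922 women (80%) are randomised, and 0.8 × 38.4 × 12 = 369 results exist.
- Both conditions at month 24: 384/24 = 16 per month. Results: 0.8 × 16 × 12 = 154, which is 0.167 of 922. Full enrolment takes 1,152/16 = 72 months. To finish by month 30 instead, the last 768 women would have to enter in 6 months: 128 per month, 8 times the earlier rate.

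**Chance of meeting the interim rule.** With t = results/922, alpha = 0.05 × t² and z = Φ⁻¹(1 − alpha), the chance is Φ((D − 0.10)/SE − z). D is the true deficit and SE is unpooled. Ranges cover control cure of 50%, 70% and 80%.

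| Results (per arm) | t | alpha | z | D = 20 points | D = 30 points |
|---|---|---|---|---|---|
| 154 (51) | 0.167 | 0.0014 | 2.99 | about 3% | 19–22% |
| 307 (102) | 0.333 | 0.0055 | 2.54 | 15–17% | 68–73% |
| 369 (123) | 0.400 | 0.0080 | 2.41 | 22–26% | 82–85% |

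Example, 50% against 20% cure:
- 51 per arm: SE = √((0.25 + 0.16)/51) = 0.0897, and Φ(0.20/0.0897 − 2.99) = 22%.
- 102 per arm: SE = 0.0634, and Φ(0.20/0.0634 − 2.54) = 73%.

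**Effect of the undefined t.** With the same 154 results but t taken as enrolment (1/3), alpha is 0.0056 instead of 0.0014. The chance at a 30-point deficit becomes 34–38%, and at 20 points 7–8%.

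**When 307 results would arrive.**
- 38.4 per month, all returns at month 12: 307/(0.8 × 38.4) + 12 = month 22.
- 38.4 per month, returns spread evenly over months 12–18 (mean lag 15): month 24 has 0.8 × 38.4 × 9 = 276 results, and 307 arrives at 307/30.72 + 15 = month 25.
- 38.4 per month, counting only closed 18-month windows: 307/30.72 + 18 = month 28, when 28/30 = 93% are randomised.
- 16 per month, returns at month 12: 307/12.8 + 12 = month 36, with 16 × 36 = 576 randomised.

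**Separate point: final power.** The plan's size is reproduced at one-sided 5%: (1.645 + 0.842)² × 0.5/0.01 = 309.3, or 310 per arm against 307 stated. At 307 per arm and 50% cure in both arms, SE = √(0.5/307) = 0.0404:
- One-sided 5%: Φ(0.10/0.0404 − 1.645) = 79.8%.
- Two-sided 95% interval: Φ(0.10/0.0404 − 1.960) = 69.8%. The same rule gives 77% at 70% cure and 87% at 80% cure.

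**The case against.** The best defence is that the text sets one date, month 24, and describes the enrolment expected by then. On that reading there are not two competing triggers. This stands. A reader might infer that the rule, followed literally, could produce a look at month 10 with no results. It could not, because such a look would break the stated date. No results at month 24 would need nobody to have been randomised in the first 12 months, which is a logical bound and not a planned outcome.

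The conflict also depends on accrual shape. Several sites may open slowly, study opening need not be the first enrolment, and recruitment is to be adjusted as the trial runs. That stands too, so the 14-month gap is conditional. But no such schedule is documented, and reaching one third only at month 24 would leave an eightfold rise in rate to finish on time. The missing count remains under any accrual.

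Perhaps one third with results was meant: at month 24 under steady accrual, 369/1,152 = 32%. That is plausible, but both sections say enrolled.

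In alpha spending, time is conventionally the information fraction. The undefined t is therefore missing detail that a sentence can settle, and on its own would be minor.

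Last, the look is non-binding and tests only for inferiority. A reader might infer that loose timing inflates the error of the final non-inferiority claim. The documents do not support that, since the look cannot produce an early claim of non-inferiority.

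**Conclusion.** The point holds in a limited form. The interim conditions do not fix the amount of information, and they are inconsistent with the plan's own 30 months if accrual is steady. Where both are met at month 24 under steady accrual, the look has about 154 of 922 results and about a one-in-five chance of meeting the rule at a true 30-point deficit. With 307 results that chance is about 70%. Even then it is only 15–17% at a 20-point deficit, so the gain is a known amount of information, not a strong stopping rule. These figures rest on steady accrual, equal arms, 20% loss and returns at month 12; later returns would lower the count at month 24.

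The harm is moderate: the action is optional, and the monitoring group meets bi-monthly and could question the timing, although no count is given to guide it. The change is worth making because the text is inconsistent as written.

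The power point stands on its own and adds no weight to the interim point. Under the stated 95% interval rule, the claim of at least 80% power fails at 50% cure, the plan's own worst case, and at 70% cure.

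**What to change.** In sections 3.2 and 12.0:

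1. Trigger the look at a stated number of randomised women with a 12-month consensus pathology result. The sponsor chooses the number; 307 is one example, being the plan's own one third applied to results.
2. Define t as observed results over planned results, and state the nominal alpha (0.0055 one-sided at 307 of 922). Use one denominator: 922 appears in 3.1 and in the sample-size text, but the test-of-cure paragraph enrols "to assure that we have 930 women with a twelve-month follow-up". The choice hardly matters numerically (0.0055 either way), but it should be fixed.
3. Reconcile the two years, the one third enrolled and the 30 months, and define study opening.

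Separately, in section 3.2, either restate the power under the 95% interval rule (about 70% at 50% cure), or state that the final rule uses a one-sided 5% bound, that is, a 90% two-sided interval.

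**Cost.** Wording only, with no extra patients or procedures in total. The real downside is timing. A trigger of 307 could put the look at about month 25 under steady 30-month accrual if returns spread over months 12–18, about month 28 if only closed windows count, and about month 36 at 16 per month (576 randomised instead of 384). The later the look, the fewer women remain for it to protect, and the sponsor should weigh this when choosing the count.
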